10.4.2 Analysis of the Primary Endpoints

Hypothesis 1: The rate of follow-up suicidal behavior will be significantly reduced among military personnel receiving CRP versus usual care risk management in addition to massed CPT.

Survival analysis with time-to-suicide attempt will be used to test overall differences between the two intervention groups. We will use the hazard ratio derived from the Cox regression supplemented with the log-rank and Wilcoxon statistics derived from the Kaplan-Meier method. Time will be calculated as number of days since the intake appointment. Multiple suicide attempts within participants will be handled using the Andersen-Gill counting process model (Anderson & Gill, 1982), which assumes that the time increments between multiple suicide attempts can be explained by past suicide attempts (e.g., shorter time intervals between suicide attempts are more likely among patients who have previously attempted suicide). **Power Analysis:** Power calculations for H1 were conducted using PROC POWER in the SAS 9.4 software. Anticipated suicide attempt rates were based on previously published clinical trials conducted within and external to the military. In previous studies of cognitive behavioral therapies for suicide prevention, the suicide attempt rate in the usual care conditions often ranges from 40-50% during the first year and active suicide-focused interventions typically have 50% lower suicide attempt rates (Brown et al., 2005; Gysin-Maillart et al., 2016; Linehan et al., 1991; Rudd et al., 2015). In our previous RCT of CRP versus usual care ([name] et al., 2017), participants receiving CRP were 76% less likely to attempt suicide. Results of our pilot study of massed CPT yielded a similar 73% reduction in suicide attempts in the CRP group versus usual care. We therefore estimated statistical power for hazard ratios ranging from 0.50-0.75 when suicide attempt rates in usual care ranged from 30-50%, assuming 15% attrition, 1-year follow-up, and a two-tailed $p<.05$. $N=150$ yielded $>80\%$ power under nearly all conditions.

Hypothesis 2: Reductions in the severity of suicidal ideation will be significantly larger among military personnel receiving CRP versus usual care risk management.

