window (up to 42 EMA surveys per participant) for each participant: stability (i.e., the autocorrelation of scores over time), severity (i.e., mean score across all responses), and variability (i.e., the root mean square successive difference [RMSSD] across all responses). Each change index will be entered as an independent variable into a linear regression model predicting pre-post change in SSI score and a binary logistic regression model predicting follow-up suicidal behavior. To evaluate the specificity of these findings to the two weeks of active treatment, we will expand these analyses to include all 5 weeks of planned EMA data collection (i.e., 1 week prior to treatment start, 2 weeks of treatment, 2 weeks after treatment completion). This approach will allow us to distinguish treatment-specific patterns from more general patterns that signal treatment response and treatment relapse. **Power Analysis:** Power calculations for H3 were conducted using G*Power 3.1.9.2 (for suicidal ideation) and PROC POWER in the SAS 9.4 software (for suicide attempts). For the linear regression model, N=150 yielded 80% power to detect a medium effect ($R^2=0.06$) and for the binary logistic regression, N=150 provided >80% power to detect an odds ratio=1.5, assuming a conservative 20% of participants attempts suicide during follow-up.

Exploratory Research Question 1: Which subjective, objective, and treatment-related factors are most useful for predicting treatment response (i.e., change in severity of suicidal ideation) and treatment relapse (i.e., follow-up suicidal behavior)?

We will use the same analytic approach described for H3 but extend the analyses to all other variables assessed via EMA (i.e., positive and negative affect, negative thinking, and maladaptive behaviors) and Fitbit (i.e., physical activity, sleep quality). We will construct a series of models to determine which variables (and combination of variables) maximize the variance explained in pre-post change in SSI score and follow-up suicidal behavior. **Power Analysis:** Power calculations for RQ1 were conducted using G*Power 3.1.9.2. Assuming our model includes no more than 6 predictor variables, N=150 yielded 80% power to detect R^2 increases of 0.06-0.08 associated with each additional predictor variable.

Hypothesis 4: More frequent CRP use will be correlated with reductions in suicide attempts and suicidal ideation.

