We will sum the number of EMA responses during which participants endorsed the use of their CRP (and safety plan), such that higher values indicate more frequent intervention use. This count variable will be entered into a Cox regression model predicting time to suicide attempt and a linear regression model predicting change in SSI score to assess the correlation of intervention use with, respectively, follow-up suicidal behavior and severity of suicidal ideation. We will construct separate models for each treatment group. To test the specificity of our findings to CRP, we will repeat these analyses with CPT homework completion, also assessed during EMA and calculated as the sum of positively endorsed EMA responses, entered as a covariate. **Power Analysis:** The power analysis for H4 mirrors the power analysis for H3 above.

Exploratory Research Question 2: Which treatment components and design features do participants find most helpful for reducing suicidal ideation and attempts?

We will use descriptive statistics of participant characteristics, chi-squared tests, and Pearson correlations (where applicable) to explore relationships among personal experiential themes, group experiential themes, and participant characteristics. **Power Analysis:** Recommendations for minimum sample size in qualitative studies using IPA typically range from 2-25 participants, depending on the homogeneity that exists within participants' lived experience (Alase, 2017; Smith et al., 1999). Because we plan to interview all enrolled participants, our sample size will be more than adequate.

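### H3 and RQ1 use binary logistic regression for follow-up suicidal behavior, which cannot directly use partial follow-up; Cox regression, already used for H1 and H4, can, for a modest gain and a change of wording

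*Protocol*

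**What the plan says.** All the statements are in Protocol section 10.4.2 unless noted.

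- **H3.** The EMA indices of suicidal ideation are entered into "a binary logistic regression model predicting follow-up suicidal behavior". RQ1 takes over the same approach for further EMA and Fitbit variables.
- **H3 power.** The plan states that "N=150 provided >80% power to detect an odds ratio=1.5", "assuming a conservative 20% of participants attempts suicide during follow-up". It mentions no attrition and does not say on what scale the odds ratio is expressed.
- **H1.** "Survival analysis with time-to-suicide attempt will be used to test overall differences between the two intervention groups", with the clock running from the intake appointment. Its power is computed "assuming 15% attrition, 1-year follow-up, and a two-tailed $p<.05".
- **H4.** "This count variable will be entered into a Cox regression model predicting time to suicide attempt". The text says that its two models address "respectively, follow-up suicidal behavior and severity of suicidal ideation", so the Cox outcome carries the same name as the H3 outcome. No time origin is given for H4. On power: "The power analysis for H4 mirrors the power analysis for H3 above".
- **Missing data (section 10.4.1).** Little's test and pattern-mixture models are named, the latter for longitudinal results. Follow-up continues for participants who stop therapy early.

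**The concern.** Section 10.4.2 gives one named outcome two model families and gives no reason. For H3 the choice matters because the protocol itself expects losses. A participant lost at week 26 without an attempt has contributed half a year of attempt-free observation. Cox regression uses that time and censors it. Ordinary logistic regression needs a yes or no at one year, so such a participant is dropped, counted as a non-event, or handled by an added device such as weighting or imputation.

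Only participants lost before any recorded attempt raise the problem; an attempt recorded before loss is classified correctly. At stake are some power in an analysis that has little to spare and, under some handling rules, the size of the odds ratio for the early-marker result. The second risk is larger if loss is related to ideation severity during treatment. That is plausible: section 8.2 allows discontinuation for events, for a need for other treatment, or for non-compliance. The documents give no figure for it.

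**Working it through.** **Inputs from section 10.4.2:** N=150; odds ratio 1.5; 20% with an attempt; two-sided 0.05; 15% attrition (stated for H1 only). **Assumptions:** the odds or hazard ratio is per 1 SD of a continuous index; where loss is related to the predictor, dropout odds double per SD.

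**Step 1: the plan's own figure.** For logistic regression with one continuous predictor (Hsieh's approximation), power = Φ(√(N·p·(1−p))·ln OR − 1.96).
- N=150: √(150×0.20×0.80) = √24 = 4.899; 4.899×0.4055 = 1.986; Φ(1.986 − 1.960) = **51.1%**, not above 80%.
- N=127.5 (15% removed): √20.4 = 4.517; 4.517×0.4055 = 1.831; Φ(−0.129) = **44.9%**.
- N for 80% power: (1.960+0.842)²/(0.16×0.4055²) = 298.4, so 299; 299/0.85 gives 352.
- Smallest odds ratio with 80% power at N=150: exp(2.802/4.899) = 1.77.
- The stated power would be reached only if the odds ratio is per unit of an index with SD about 1.41 (0.572/0.4055), which the protocol does not say.

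**Step 2: Cox in closed form.** Power = Φ(√d·ln HR − 1.96), with d the number of events.
- No loss: d = 150×0.20 = 30; 5.477×0.4055 = 2.221; Φ(0.261) = 60%.
- All lost participants contributing no events: d = 30×0.85 = 25.5; 5.050×0.4055 = 2.048; Φ(0.088) = 53%.

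**Step 3: simulation with losses.** N=150, true hazard ratio 1.5 per SD, 15% lost, at least 1,000 simulated trials per setting (simulation error up to √(0.25/1,000), about 1.6 points). With complete data, a hazard ratio of 1.5 corresponds to an odds ratio of about 1.60 at 20% events and 1.66 at 30%.

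| Setting | Cox | Logistic, complete cases | Logistic, losses as non-events | Logistic, only event-free losses excluded |
|---|---|---|---|---|
| 20% events, loss unrelated | 56% | 50% | about 2–3 points below Cox | almost no bias |
| 20% events, dropout odds ×2 per SD | 53%, HR 1.51 | 46%, OR 1.59 | about 40%, OR 1.48 | OR 1.71 |
| 30% events, dropout odds ×2 per SD | 72%, HR 1.51 | 63%, OR 1.66 | 57%, OR 1.52 | 79%, OR 1.78 |

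The Cox hazard ratio stays at 1.50 to 1.51 throughout. Complete-case logistic regression keeps the right odds ratio because loss depends only on the predictor in the model. The 79% in the last column is not a gain: it comes with an inflated odds ratio.

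**Step 4: another loss mechanism.** With a hazard ratio of about 1.45 per SD, 20% events and a dropout hazard that doubles per SD, the complete-data odds ratio is 1.54. Losses as non-events give 1.37 (power 28%). Excluding event-free losses gives 1.67 (57%). Cox gives HR 1.46 (49%). With unrelated loss, the odds ratios are 1.53 to 1.54 against 1.55 with complete data. The direction is the same; the size depends on the mechanism.

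**The case against.** Logistic regression is a legitimate model for whether a participant relapses, which is the question behind a clinical decision tool. A rule for participants lost early commonly sits in a statistical analysis plan, which is not shown here, and weighting or imputation would be available. Follow-up continues after therapy stops (section 10.4.1), and section 8.1 has the team attempt the planned assessments, so stopping therapy is not loss. The 15% figure comes from the H1 power paragraph. If loss is unrelated to the predictor, bias is negligible under any of the rules.

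All of this stands, and it rules out several stronger readings that a reader might infer:
- That logistic regression must misclassify or drop people. It need not; it only lacks a direct way to use partial follow-up.
- That dropping the losses biases the odds ratio as surely as miscoding them does. Complete-case analysis is unbiased when loss depends only on the modelled predictor; it loses power.
- That H3 contradicts H4, or that an odds ratio beside a hazard ratio spoils a planned comparison. The protocol plans no such comparison.
- That H4 already starts its clock after the EMA window. It states no origin, and H1 counts from intake.

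What the objection does not remove is that the protocol itself fixes the weaker model, while the attempt dates that Cox regression needs are already required for H1.

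**Conclusion.** The point holds as an improvement to the analysis, not as an error that invalidates H3. For N=150, a hazard ratio of 1.5 per SD and 15% loss, Cox regression gains about 5 to 9 points of power over complete-case logistic regression. Against counting losses as non-events, it gains about 2 to 3 points with unrelated loss. If dropout odds double per SD, the gain is about 12 to 16 points, and that rule also attenuates the odds ratio (1.60 to 1.48 at 20% events). Excluding only event-free losses inflates it (1.60 to 1.71) in that case. The predictor–dropout link is an assumption; without it the bias is negligible.

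Cox does not rescue the stated power. The figure above 80% computes to about 51% if the odds ratio is per SD, and Cox reaches about 53 to 56% for a hazard ratio of 1.5, which is a slightly larger effect than an odds ratio of 1.5.

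**What to change.** In section 10.4.2, for H3 and RQ1:

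1. Replace the logistic model with Cox regression of time to first suicide attempt, censoring at last contact.
2. Start the risk period at the end of the EMA window used for the predictor: after the two treatment weeks for the main analysis, and later for the analysis that uses the full EMA period. This is a new specification. It keeps the predictor ahead of the outcome; attempts inside the window should be reported separately. State the H4 time origin too.
3. Keep logistic regression as a sensitivity analysis if a yes/no summary is wanted, with its rule for early losses written down.
4. Restate the H3 power for a hazard ratio, giving the predictor scale and allowing for attrition. H4 borrows this power statement, so it would then have a basis that matches its model, although H4 fits each arm separately and needs its own numbers.

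The cost is wording and a recalculated power statement; no new data are needed. The downsides are that the result is a hazard ratio, that proportional hazards must be checked, and that censoring must be unrelated to attempt risk given the predictors in the model.

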9.2 STUDY EVALUATIONS & PROCEDURES

9.2.1 Visits and Procedures

Visits: See Table in Section 1.2 (Visit Schedule Study Procedures and Assessments) for Study Visits.

Procedures:

- Individuals referred by their provider for consideration of the study or who self-refer in response to study advertisements will have a brief discussion with a member of the study team where the basic study inclusion and exclusion criteria will be reviewed to help the individual determine if he or she meets the study criteria or has obvious exclusions from the study protocol so as to prevent individuals from taking unnecessary time for consent and more in-depth screening.
- Following consent, participants will complete the baseline assessment. The baseline assessment will include questionnaires and interviews and will last 2-3 hours in total.
- Once confirmed eligible, the participant will be randomly assigned into one of the two study arms, Crisis Response Planning (CRP) or Treatment as Usual (TAU). Regardless of which study arm the participant is randomized to, all participants will receive Massed Cognitive Processing Therapy (mCPT). This information will be conveyed to the participant during a 1½ -hour Intake Appointment. During this appointment additional questionnaires will be completed either on paper or on the computer. Also at this time, the participant will sync their Fitbit or a Fitbit provided by the study staff with Fitabase and load the EMA app onto the participant's phone. The data collection through Fitabase and EMA prompts will start at this time and continue for 28 days.
- CPT sessions will be scheduled daily for 10 consecutive business days (i.e., “massed” CPT), with the first appointment being 1-2 weeks post-intake. Participants will be allowed to schedule up to 3 optional “booster sessions” during the follow-up year to review skills learned in therapy and receive additional support and/or coaching after the acute treatment. Each of the 10 treatment sessions and up to 3 optional booster sessions will last 1-hour.
- Within 1 month of ending therapy, participants will complete one 45–60-minute semi-structured interview with study staff.
- Follow-up assessments will be completed 4-, 13-, 26-, 39-, and 52-weeks following treatment. Each follow-up will last 30-45 minutes.

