Mixed effects regression models with repeated measures will be used to test group differences in suicidal ideation over time. Treatment group, time, and the treatment*time interaction will be entered as independent variables and SSI scores as the outcome. Random intercepts and slopes will be tested, and covariance structures will be selected by comparison of likelihood criteria (e.g., Akaike's Information Criteria). Group differences in mean SSI scores will be probed at 2, 4, 13, 26, 39, and 52 weeks, with the largest differences between groups expected to occur at 2 and 4 weeks. Consistent with these expectations, we will also compare the SSI slopes from baseline to session 5 (treatment midpoint) and session 10 (treatment end) to determine if the rate of change in suicidal ideation differs across groups.

Power Analysis: We used the General Linear Mixed Model Power and Sample Size (GLIMMPS) software to calculate power for H2 using data from our pilot study to estimate SSI mean differences between groups at baseline ($M_{diff}=0$), treatment midpoint ($M_{diff}=4$), and treatment end ($M_{diff}=2$) assuming a two-tailed $p<.05$. Results indicated $N=150$ provided 81% power.

Hypothesis 3: Less severe suicide risk features during treatment will predict treatment response (i.e., change in severity of suicidal ideation) and treatment relapse (i.e., follow-up suicidal behavior).

For H3, we will use suicidal ideation EMA ratings collected during the 2 weeks of massed CPT. We will first calculate the following indices of change in suicidal ideation during the entire 2-week observation

Abbreviated Title: mCPT+CRP

Version Date: 07/10/25

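### Minor: the H3 and RQ1 relapse outcome has no start date, so the expanded analysis counts attempts made while its EMA predictor is still being recorded

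*Protocol*

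**What the plan says.** All of the following is in the protocol.

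- **H1 (Section 10.4.2).** The hypothesis reads "The rate of follow-up suicidal behavior will be significantly reduced among military personnel receiving CRP". For its survival model, "Time will be calculated as number of days since the intake appointment".
- **H3 (Section 10.4.2).** The same outcome term is equated with relapse: "treatment relapse (i.e., follow-up suicidal behavior". For the predictor, "we will use suicidal ideation EMA ratings collected during the 2 weeks of massed CPT". The attempt outcome is analysed by "a binary logistic regression model predicting follow-up suicidal behavior", with no date from which attempts count.
- **Expanded H3 analysis (Section 10.4.2).** The predictor is extended to five weeks: "1 week prior to treatment start, 2 weeks of treatment, 2 weeks after treatment completion".
- **RQ1 (Section 10.4.2).** "We will use the same analytic approach described for H3", extended to the other EMA variables and to Fitbit.
- **Visits (Section 9.2.1).** "Follow-up assessments will be completed 4-, 13-, 26-, 39-, and 52-weeks following treatment". The first CPT session falls 1 to 2 weeks after intake. EMA starts at intake and runs for 28 days.
- **Recording of attempts (Sections 1.2 and 9.2.1).** Selected SITBI-R items are self-reported at intake and at weeks 1 and 2, asking about the time since the last assessment. Attempts before and during treatment will therefore be in the data.

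**The concern.** Aim 2 looks for early markers of relapse, so the marker has to be measured before the event. An attempt made while EMA is running can change the ratings that follow it. The severity and variability indices may then partly reflect an attempt that has already happened, yet be reported as having predicted it. An association of that kind has no forward value for a clinician.

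The expanded analysis has this overlap as printed. The two-week analysis has it only on one reading of follow-up, and the two readings give different sets of events for the same hypothesis. The SSI-change outcome is not touched by this point.

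**Working it through.** **1. Timeline, in days from intake.** Session 1 falls on day 7 to 14. Ten consecutive business days take 11 to 13 calendar days from first to last session (one or two weekends crossed). Session 10 is therefore on day 7 + 11 = 18 to 14 + 13 = 27. The expanded EMA window opens a week before session 1 (day 0 to 7) and closes 14 days after session 10 (day 32 to 41).

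**2. Order of predictor and outcome.**

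| Analysis | EMA window closes | Outcome from intake | Outcome from end of treatment |
|---|---|---|---|
| Two-week | day 18–27 | overlap up to session 10 | no overlap |
| Expanded | day 32–41 | overlap up to day 32–41 | overlap for 14 days |

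Only the two-week analysis depends on the reading. If EMA really stops on day 28, the post-treatment overlap in the expanded analysis shrinks to 28 − 27 = 1 day up to 28 − 18 = 10 days, but does not vanish.

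**3. Events involved.** The H3 power statement assumes that 20% of 150 attempt suicide, which is 30 events. The protocol gives no timing, so I spread them evenly (assumption) from intake to 52 weeks (364 days) after session 10, a span of 382 to 391 days.

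- Two-week, intake reading: 30 × 18/382 = 1.4 to 30 × 27/391 = 2.1.
- Expanded, intake reading: 30 × 32/382 = 2.5 to 30 × 41/391 = 3.1.
- Expanded, post-treatment reading: 30 × 14/364 = 1.2 (0.1 to 0.8 if EMA stops on day 28).

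A constant hazard, 150 × (1 − 0.8^(d/T)) with T = 365 or 393 days, gives slightly more: 2.4–2.6 by day 28, 3.0–3.2 by day 35, and 3.5–3.7 at the outer edge, day 41.

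**4. Bias in the mean-severity index.** Simulated with N = 150, 20% events and a marker with no forward value. The shares of early attempts and the sizes of the shift are assumptions.

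- *Every early attempter shifted over the whole window.* With 8%, 15% and 30% of attempts early and a 1 SD shift, the 5% test rejects 8%, 10% and 29% of the time (mean odds ratio 1.08, 1.15, 1.33). With 0.5 SD it rejects 5%, 5% and 11%. Counting only later attempts gives 4–5% throughout.
- *Shift applied only to the part of the two-week window after the attempt*, attempts uniform from intake to session 10. This is more realistic, since an attempt cannot alter ratings already given. With 6%, 10% and 20% early, rejection is 5.1%, 6.1% and 10.4% for 1 SD, and 8.5%, 11.8% and 30.2% for 2 SD. At 20% early the odds ratio is 1.16 or 1.31. Simulation error near 5% is √(0.05 × 0.95/1500) = 0.6 points.

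For the expanded window on the post-treatment reading, an attempt can affect at most 14/35 = 40% of the ratings, 20% on average. A 1 SD rise afterwards then moves that person's mean by about 0.2 SD, well below the 0.5 SD case. The autocorrelation and variability indices were not simulated.

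**5. Power cost of dropping early events.** For an odds ratio per SD, power = Φ(√(N·p·(1−p)) × ln OR − 1.96). With 30 events and OR 1.5: √24 × 0.405 − 1.96 = 0.03, or 51%. The protocol states more than 80%. That would need a predictor SD of about 1.41 units, or an OR of about 1.77 per SD. The unit is not stated, so I use the formula only for comparison. With 27.5 events power is 48%, with 24 events 44%, with 21 events 41%.

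**The case against.** The best defence is that follow-up already means after treatment. Section 9.2.1 places the follow-up assessments after treatment and contrasts follow-up appointments with intake and weeks 1 and 2. The synopsis separates treatment from follow-up, and an attempt before session 1 is hardly a treatment relapse. The H1 sentence on intake sets the time axis of H1's survival model; nothing in the H3 text imports it. This stands for the two-week analysis, whose time order is right on that reading. It does not help the expanded analysis, whose predictor runs two weeks into the post-treatment period.

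A second defence is that exact event windows for a secondary aim usually go in the SAP. That is fair for the missing date alone and is one reason to rate the point low. But the protocol itself sets the expanded window and the outcome, and these two overlap.

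Two stronger readings are tempting. A reader might infer that the main H3 analysis necessarily counts attempts before or during treatment; the text permits that reading but points the other way. A reader might also infer serious false-positive inflation. Rejection rates of 17–43% and odds ratios of 1.23–1.44 can be produced, but only by assuming that 20% of attempts precede session 10 and that each raises the whole-window mean by 1 to 2 SD. The documents give neither figure, and the whole-window shift overstates what an attempt partway through can do.

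**Conclusion.** The point holds in limited form. The expanded H3 analysis, and RQ1 where it follows it, lets attempts count as outcomes while the predictor is still being recorded, on either reading of follow-up. For the two-week analysis the protocol is ambiguous, not wrong.

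About 1 to 3 of 30 events are involved if attempts are evenly spread (just under 4 in the widest constant-hazard case), and the expected bias is then small. Material bias needs early clustering together with a large shift in ratings. Early clustering is plausible, because eligibility requires active ideation in the past week or suicidal behavior in the preceding month, but the protocol does not quantify it. Severity is minor: this is a secondary aim, and the H1 comparison is unaffected.

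**What to change.** 1. For H3 and RQ1, define the outcome as a suicide attempt after the last EMA day used in that model: after session 10 for the two-week analysis, after the last EMA day for the expanded one. Start risk at that landmark.
2. Do not count earlier attempts as outcomes. Describe them, and add them as a history covariate only if numbers allow; with about 2 such participants in 150 the estimate would be unstable.
3. Give this outcome its own name, such as post-treatment suicide attempt, and leave H1 counted from intake.
4. Reconcile the EMA period: 28 days from intake in Sections 1.2 and 9.2.1, five weeks in Section 10.4.2. The expanded landmark depends on it. A fixed day-28 landmark would not remove the overlap for a window that closes on day 32 to 41.

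The cost is protocol wording, one date filter, and about 2 to 3 of 30 events at constant hazard (power from 51% to about 48% on the per-SD comparison above). If 20% or 30% of attempts fall before the landmark, 24 or 21 events remain.

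### Hypothesis 3 judges specificity to treatment by widening the window to one that still contains the treatment weeks, so the check has little ability to separate a treatment-specific marker from a general one

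*Protocol*

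**What the plan says.** Protocol section 10.4.2, Hypothesis 3, fixes the main window: "For H3, we will use suicidal ideation EMA ratings collected during the 2 weeks of massed CPT". Three indices are computed for each participant: stability (an autocorrelation), "severity (i.e., mean score across all responses), and variability (i.e., the root mean square successive difference [RMSSD] across all responses"). On the models it says: "Each change index will be entered as an independent variable into a linear regression model predicting pre-post change in SSI score". A logistic model for follow-up suicidal behavior runs alongside.

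The specificity check follows. The protocol says "To evaluate the specificity of these findings to the two weeks of active treatment, we will expand these analyses to include all 5 weeks" and spells the window out as "1 week prior to treatment start, 2 weeks of treatment, 2 weeks after treatment completion". It then states what the check will deliver: "This approach will allow us to distinguish treatment-specific patterns from more general patterns that signal treatment response and treatment relapse".

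It describes no index for the non-treatment weeks alone, no model holding two phases together, and no rule for comparing the two-week and five-week results.

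**The concern.** The five-week window includes every response in the two-week window. If only ideation during treatment carries information, the five-week index still predicts outcome, because 2/5 of it is the treatment period. If a stable personal level carries the information, both indices predict. The expected finding is the same in kind under either explanation, and only the degree of attenuation differs.

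What is at stake is a supporting claim under Aim 2. A reader who sees both windows predict may conclude that the marker is general, and one who sees only the two-week window predict may conclude that it is specific to treatment. Neither conclusion would be well founded. Exploratory Research Question 1 adopts the Hypothesis 3 approach for the other EMA and Fitbit variables, so the same check may be carried over to them.

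**Working it through.** **The plan's own figure.** The protocol states "N=150 yielded 80% power to detect a medium effect" (R²=0.06, two-sided alpha 0.05). With noncentrality 150×0.06/0.94 = 9.57, the F test gives power of 0.867 with one predictor, 0.789 with two and 0.728 with three. With one predictor and N=127 (15% attrition, the rate stated for Hypothesis 1) it gives 0.807. Two standard variants thus come within two points of 80%. That figure is not in dispute, and N=150 and R²=0.06 are used below.

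**Inputs.** Treatment window 2 weeks and extended window 5 weeks (section 10.4.2). EMA elsewhere is 28 days from intake (sections 1.2 and 9.2.1), so W=4 is shown beside W=5. The correlation *r* between weekly means is not in the documents. It is assumed, over 0 to 0.8, equal for all pairs of weeks and with equal weekly variance.

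**Step 1: part against whole.** For the mean index,

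corr(2-week, W-week) = √{ [(1+(W−1)r)/W] / [(1+r)/2] }.

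- r=0: √(0.20/0.50) = 0.63 for W=5; √(0.25/0.50) = 0.71 for W=4.
- r=0.3: √(0.44/0.65) = 0.82; √(0.475/0.65) = 0.85.
- r=0.6: √(0.68/0.80) = 0.92; √(0.70/0.80) = 0.94.

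At r=0 this is overlap alone: 40% shared variance for five weeks, 50% for four. In simulated series with no true differences between persons, RMSSD gave 0.63–0.64 (five weeks) and 0.70–0.71 (four weeks), and the autocorrelation gave 0.60–0.62 and 0.67–0.69. The problem is therefore not confined to the mean.

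**Step 2: without overlap.** Against all non-treatment weeks of the five-week window, the correlation is r/√{[(1+r)/2]·[(1+2r)/3]}: 0, 0.51 and 0.78 at r = 0, 0.3 and 0.6. Against a single pre-treatment week it is r/√[(1+r)/2]: 0, 0.37 and 0.67.

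**Step 3: can the check tell the two explanations apart?** If only the treatment weeks matter (R²=0.06), the five-week index has R² = 0.06 × (Step 1 correlation)². For r = 0.25, 0.5 and 0.8 that is 0.06×0.64 = 0.038, 0.06×0.80 = 0.048 and 0.06×0.933 = 0.056. Simulation (4,000 trials, N=150) gives the share of trials with a significant five-week result among those with a significant two-week result. In the trait case, the trait itself explains 6% of outcome variance.

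| r between weeks | Only treatment weeks matter | General trait |
|---|---|---|
| 0.25 | 75% | 93% |
| 0.5 | 88% | 97% |
| 0.8 | 95% | 98% |

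A formal test of the two-week against the five-week correlation (Williams' test) rejects in only 6–17% of trials.

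**Step 4: separate phases in one model.** With treatment and non-treatment indices entered together, and only the treatment weeks mattering, the treatment coefficient is significant in 78%, 58% and 25% of trials at r = 0.25, 0.5 and 0.8. The non-treatment coefficient stays near nominal (5.3%, 5.7%, 5.1%). Under the general trait, the treatment coefficient is significant in 19%, 14% and 8%. This exceeds 5% because each phase measures the trait with error and adjustment is incomplete.

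**The case against.** The strongest reply is that the sentence lists three phases and may mean that each will be analysed separately, with coding details left to an analysis plan that is not shown. That reading is possible. It is not what expanding the analyses to all five weeks says, however, and the protocol fixes both the method and the inference it will draw. If separate phases were meant, one sentence would settle it.

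Three limits on the criticism stand:

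- Overlap alone accounts for only 40–50% of shared variance. The higher correlations rest on an assumed between-week correlation and reflect real stability between persons.
- A reader might infer that the check can show nothing. That goes too far. Some attenuation is expected if the marker is specific to treatment. At r=0.25 the five-week result is lost in 25% of trials with a significant two-week result, against 7% under a general trait. The gap narrows to 12% against 3% at r=0.5 and 5% against 2% at r=0.8.
- A reader might also infer that Hypothesis 3 or Aim 2 fails. The documents do not support this. Aim 2 asks for early markers of response and relapse, not for a signal beyond the patient's usual level, and the two-week models address Hypothesis 3 directly.

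**Conclusion.** The point holds in limited form. On the plain reading, the check sets a window against a longer one that contains it, and at the protocol's own N and effect size agreement between them is the usual result under either explanation (about 75–95% against 93–98%). The stated ability to distinguish treatment-specific from general patterns is therefore not supported. The accurate description is low power to discriminate, with no comparison rule to use what information there is.

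The correlations assume equal weekly variances and a common between-week correlation that the documents do not give. The part-whole structure itself needs no assumption. The two-week Hypothesis 3 models, Hypotheses 1 and 2, the sample size and trial conduct are untouched.

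**What to change.** Compute each index separately in non-overlapping phases: pre-treatment, treatment, and whatever post-treatment EMA days are actually collected. With 28 days from intake, session 1 one to two weeks later and 14 days of treatment, 28−7−14 = 7 down to 28−14−14 = 0 post-treatment days remain, so the protocol should first reconcile its five weeks with its 28 days.

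Enter the treatment-phase index and the pre-treatment (or non-treatment) index in the same model, and read specificity from the treatment-phase coefficient adjusted for the other phase. Hypothesis 4 already handles specificity this way, by adding a covariate. Do not test the two coefficients for equality unless the windows have equal length or the indices are standardised, since phases of different length differ in reliability. Reword the claim that the approach will distinguish the two patterns so that it matches what this model can show.

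No data collection changes. The cost is wider intervals and limited power when ideation is very stable between weeks (78%, 58% and 25% in Step 4), so a null adjusted coefficient should not be read as evidence that a marker is non-specific. A significant one should be read with the incomplete adjustment in mind.
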